Understanding the validity of NDBI targets across diverse populations will help match interventions to increasingly diverse populations in the U.S. In the U.S. African American and Hispanic/Latino children are diagnosed and access services at a later age as compared to Caucasian children. The majority of states have passed legislation that mandates insurance benefits for early intervention and there are increasing efforts to implement NDBIs in diverse communities. However, knowledge of how to tailor these interventions to diverse communities is incomplete. As such, the R21 aligns with NIMH Strategic Objective 4: To strengthen the public health impact of NIMH-supported research; and objectives of the Federal Interagency Autism Coordinating Committee Strategic Plan: To reduce disparities in early detection and outcomes for underserved populations.

Design & Procedures

The R21 will build on collaborations and infrastructure established in [name] NIMH K01. The K01 aims to adapt a caregiver coaching version of the Early Start Denver Model (ESDM), an NDBI and the first empirically-validated comprehensive intervention for toddlers with ASD, for implementation by non-specialists in South Africa. Following a significant amount of formative work and capacity building, a pilot study will begin in January 2019, and enroll 20 ASD caregiver-child dyads from culturally diverse, low-resource backgrounds.

The R21 will evaluate NDBI child, caregiver-child, and caregiver treatment targets, and a digital outcome measure of treatment response. The study design will include both a baseline cross-sectional phase and a longitudinal pre-post phase, nested within the ongoing K01. The R21 will extend ASD group recruitment by 1 year, allowing for 30 ASD caregiver-child dyads to be recruited in total. In addition, the R21 will facilitate recruitment of 30 children with developmental delay and 30 with typical development

who, along with the ASD group, will participate in the baseline cross-sectional phase of the study. The ASD group will then participate in the longitudinal pre-post phase of the study, where they will receive 12 NDBI-informed caregiver coaching sessions delivered by non-specialists.

COVID-19 adaptations: Transition to telehealth will only occur for the ASD group who receive the caregiver coaching intervention. Baseline assessments of the TD and DD group will be on hold until COVID-19 in-person restrictions are lifted by the University of Cape Town IRB.

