In the baseline cross-sectional phase 30 caregiver-child dyads with ASD, 30 with typical development, and 30 with developmental delay will be recruited. ASD caregiver-child dyads will continue to be recruited from Western Cape Department of Education Autism Schools (as per K01 recruitment approach). Children with developmental delay will be recruited from Neurodevelopmental Clinics at Red Cross Children's Hospital. Children with typical development will be recruited from Early Childhood Development Centers. Inclusion criteria are as follows: (1) the child is between 18 and 72 months of age; (2) the subject’s family speak isiXhosa, isiZulu, Afrikaans, or English (~ 97% of all household languages spoken in the Western Cape province); (3) the child’s ethnicity/race is African or Coloured (a South African term for mixed race); and (4) the child lives within an area served by the recruitment sites. Additional inclusion criteria are group specific. For the ASD group: (1) the child meets criteria for an ASD diagnosis based upon DSM-5 criteria and informed by the ADOS-257 administered by research reliable raters; and (2) the caregiver is \geq 18 years old. For the developmental delay group: (1) the child screens positive on the Ten Questions; (2) screens negative on the autism behavior checklist (ABC); and (3) has been diagnosed with developmental delay by a developmental pediatrician. For the typically developing group: The child (1) screens negative for a developmental delay on the Ten Questions; and (2) screens negative on the autism behavior checklist (ABC).

COVID-19 adaptations: Because we aim to assess the acceptability, feasibility, and appropriateness of the adapted telehealth coaching intervention - views of multiple stakeholders involved in the implementation of the intervention will be assessed. This includes the child's caregiver, Early Childhood Development Practitioners, Early Childhood Development Practitioner School Supervisors, and ESDM therapists who provide supervision and oversight of the caregiver coaching session. Inclusion criteria are as follows: For the Early Childhood Development Practitioners (n=2) and Early Childhood Development Practitioner School Supervisors (n=2) group: the ECD worker and/or school supervisor are 1) employed by our participating recruitment partners (Western Cape Education Department Schools) and 2) involved in delivery of the caregiver coaching sessions, either in person or

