Remote baseline assessments will include questions about demographics; questions about technology use; a caregiver-child interaction that will be recorded on the caregivers' smart phone and uploaded to a HIPPA compliant Duke Box folder; and the VABS-3. Audio-recorded individual interviews will be conducted with caregivers in the ASD group at baseline to assess family routines and strategies they use to interact with their child. In addition, these caregivers will complete the Family Routines Inventory. Remote post-intervention assessment in the ASD group will include a caregiver-child interaction will be recorded on the caregivers' smart phone and uploaded to a HIPPA compliant Duke Box folder; and the VABS-3. Following each telephone-based coaching session a caregiver-child interaction will be recorded on the caregivers' smart phone and uploaded to a HIPPA compliant Duke Box folder. The recorded caregiver-child interactions will occur in authentic environments of the child, with every day materials that the child are caregiver are familiar with.

Once Covid-19 restrictions are lifted and the risk of seeing participants are judged as acceptable by our partner sights and University of Cape Town IRB we will offer participants a choice of in-person

caregiver-coaching delivery. Should restrictions be reinstated the above procedures and methods will be implemented as necessary.

Selection of Subjects

The proposed research will be conducted within the Cape Town metropolitan region, South Africa, in autism schools, neurodevelopmental clinics, and early childhood development centers. The (1) baseline case-control study (autism spectrum disorder: ASD; developmental delay: DD; and typical development: TD) and the (2) longitudinal pre-post design intervention study (ASD group only and their caregivers) will evaluate naturalistic developmental behavioral intervention (NDBI) treatment targets and involve 120 human subjects (30 ASD caregiver-child dyads=60, 30 DD, 30 TD). In order to account for the estimated 15% attrition, and ensure a final total sample size of 30 caregiver-child dyads in the ASD group for the pre-post phase of the study, 35 caregiver-child dyads will initially be recruited. Therefore, 130 participants total will be enrolled in the study.

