Similar recruitment procedures will be followed for the DD and TD groups, with potential subjects being identified by participating recruitment sites (Neurodevelopmental clinics at Red Cross hospital for DD group, and early childhood development centers in the Cape Town metropolitan region for TD group). If participants are interested in screening, they will be referred to the Project Coordinator who will meet with them in a private location to conduct the screening. Participants will be asked to provide oral consent to be screened. The Project Coordinator will screen participants in the DD and TD groups using the Ten Questions questionnaire and the Autism Behavior Checklist. For the DD group, the child will need to screen positive on one or more questions on the Ten Questions in order to be eligible to participate in the study, and screen negative on the Autism Behavior Checklist. For the TD group, the child will need to screen negative on all questions on the Ten Questions questionnaire, in addition to screening negative on the Autism Behavior Checklist. If a child in the TD group screens positive on the Ten Questions, the Project Coordinator (who is an occupational therapist by training) will provide the caregiver with appropriate referral information for the Neurodevelopmental clinic at Red Cross hospital. If children in the DD or TD group screen positive on the Autism Behavior Checklist, an ADOS-2 will be administered by a research reliable South African clinician to help inform decisions on whether the child has ASD. If concerns remained for ASD following ADOS-2 administration, the Project Coordinator will provide the caregiver with appropriate referral information for the Neurodevelopmental clinic at Red Cross hospital. The Project Coordinator will then screen potential subjects in the DD and TD group for additional exclusion criteria. Potential subjects who meet eligibility criteria will be informed of the study, and invited to participate.

Participants will be informed throughout the recruitment process and study sessions that participation is voluntary and that they may refuse to answer any question for any reason. In addition, the caregivers of their child may refuse to participate or withdraw from the study at any time without penalty or loss of benefits to which they are otherwise entitled.

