Frequency scores for initiation of and response to joint attention (IJA and RJA), will be derived from behavioral observations during a series of tasks presented by an examiner blind to child diagnosis. In order to assess joint engagement, child engagement states will be coded from video-recorded caregiver-child interactions and scored in a Likert scale by a trained rater, blind to child diagnosis. For joint attention and joint engagement, the primary statistical comparisons will be to evaluate whether the ASD group score lower on three co-primary endpoints: IJA and RJA for joint attention, and joint engagement. Our power calculation was based on a two-sample t-test with unequal variances, using as a reference the observed IJA scores from a similar sample of ASD and typically developing children from a Western setting. With two groups of 30, assuming mean (SD) IJA score of 16 (8) among typically developing children, we will have 90% power to detect a difference in mean scores of at least 7 between ASD and typically developing children. A similar analytic approach will be used for RJA and joint engagement. If a difference is observed, between the ASD and typically developing groups, a secondary comparison will be conducted to compare the ASD group and the developmentally delayed group, using a multiple comparisons adjustment to control for Type I error. In collaboration with experts at Duke, using digital technology, we will explore ASD behavioral risk makers indexing children's facial affective expressions, attention/orienting, and postural sway. Using the same statistical analysis approach described above, we will explore whether children with ASD show lower attention to social stimuli, consistency in orienting to name calls and positive affective response, and greater postural sway to stimuli in relation to the developmentally delayed and typically developing groups.

Because the main predictors of response are age, sex and group (ASD, DD, TD), by balancing the age and sex distribution across the three groups we will be able to better isolate differences in child joint attention, joint engagement, and ASD behavioral symptoms, between the groups that are attributable to whether the child is ASD, DD, or TD. This will answer a fundamental question of whether our NDBI treatment targets are valid. Addressing this main research question is critical to designing effective early interventions that may be adapted for pilot testing across sub-Saharan Africa.

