Our analysis will focus on graphical displays, which will be complemented by appropriate inferential statistical procedures. For the graphical displays, we will visualize the distribution of joint attention, joint engagement, and ASD behavioral symptoms in histograms to better understand the shape and spread of the distribution of each. We will overlay the shape of the distributions (e.g. as kernel density plots) in each of the three groups, using the data from the 30 children in each group, with each curve plotted in a different color. We will then move from these individual data distributions to the pairwise relationships between joint attention, joint engagement, and ASD behavioral symptoms, by plotting the values in scatterplots and color-coding the three groups. For example, with initiation of joint attention on the horizontal axis and response to joint attention on the vertical we can clearly show the distribution of joint attention and how that distribution differs by the three groups. Similarly, we will summarize joint attention, joint engagement, and ASD behavioral symptoms and covariates by the three groups (ASD, DD, TD) using means and standard deviations, median and interquartile ranges or counts and percentages, as appropriate. In terms of inference, we can compare joint attention, joint engagement, and ASD behavioral symptoms between the three groups by performing a one-way ANOVA on each, or by using the alternative non-parametric Kruskal-Wallis test, if needed. Whilst statistical inference is valuable, we anticipate that we will elicit most information through careful data visualization. If, in fact, other covariates, such as maternal education or socioeconomic status, are identified as being important we will be able to extend to a regression modeling framework in which we would separately analyze joint attention, joint engagement, and ASD behavioral symptoms, by

regressing each on group and adjusting for the additional covariates. We will be cautious about adjusting for multiple covariates given the relatively small sample size (30 per group). Nevertheless, as noted above, since age and sex are expected to be the strongest predictors, over and above group (ASD vs. DD vs. TD), we do not anticipate the need for extensive regression modeling, if any.

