In the second phase, we will conduct a longitudinal pre-post study with children in the ASD group who receive 12 sessions of intervention. In order to account for the estimated 15% attrition, and ensure a final total sample size of 30 caregiver-child dyads in the ASD group for the pre-post phase of the study, caregiver-child dyads will initially be recruited. Using digital technology, we will re-assess child social interest, orienting, attention, affect, and postural sway post-intervention and explore patterns of change in individual trajectories of these behaviors. Paired t-tests (or Wilcoxon rank-sum tests if appropriate), in conjunction with exploratory graphical analyses of individual trajectories over time, will be conducted to assess the pre versus post change following 12 sessions of NDBI-informed caregiver coaching.

When focusing on changes in ASD behavioral symptoms and caregiver strategies in the ASD group following 12 intervention sessions (exploratory component of Aim 1 and Aim 3) we will again use comprehensive data visualization with scatter plots of the pre and post-intervention measures of each outcome for the 30 ASD children. For inference, paired t-tests will be used, or if assumptions of the t-test are not met, the Wilcoxon signed rank test will be used. Additionally, given that severity (measured by ADOS-2 comparison score) may predict changes over time, we will perform stratified analyses separately for high severity from low severity children. Specifically, we will examine all data visualizations by severity category. Likewise, we will perform inference separately for the high and low severity children. We may explore regression modeling strategies where we regress change in each outcome measure on severity category (or severity score, if appropriate), a strategy that would allow us to additionally adjust for age and/or sex. Nevertheless, we recognize that with a total sample size of 30, we will be cautious when performing and interpreting our inferential statistics and, if modeling assumptions are not satisfied, we will not proceed with the analysis. As noted above, data visualization and summary statistics will provide us with a wealth of information.

Aim 2: In the ASD group, determine the caregiver-child context for South African dyads, by identifying common family routines and characteristics of caregiver-child dyadic exchanges.

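### Age and sex are named as the strongest predictors besides group, but no recruitment step balances them and the ASD-TD and ASD-DD comparisons do not adjust for them.

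*Combined protocol and SAP*

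**What the plan says.** In Data Analysis & Statistical Considerations, Aim 1, the plan names age, sex and group as the main predictors of response and states that "by balancing the age and sex distribution across the three groups we will be able to better isolate differences". It later repeats that age and sex should be the strongest predictors after group, and concludes that "we do not anticipate the need for extensive regression modeling, if any".

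The planned comparisons in that section are:
- ASD v TD on three co-primary endpoints (IJA, RJA, joint engagement), with power based on a two-sample t-test with unequal variances.
- ASD v DD, only if ASD and TD differ, with a multiplicity adjustment.
- One-way ANOVA or Kruskal-Wallis across the three groups.

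None has an age or sex term. Regression is offered on a different condition: "If, in fact, other covariates, such as maternal education or socioeconomic status, are identified as being important". Adjustment for age and sex is mentioned only for the pre-post change within the ASD group, as "a strategy that would allow us to additionally adjust for age and/or sex".

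On recruitment, Design & Procedures takes ASD dyads from autism schools and DD children from hospital neurodevelopmental clinics, and says "Children with typical development will be recruited from Early Childhood Development Centers". Subject Recruitment and Compensation adds: "Similar recruitment procedures will be followed for the DD and TD groups, with potential subjects being identified by participating recruitment sites". The common age range is 18 to 72 months. Selection of Subjects calls the baseline phase a case-control study.

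**The concern.** The argument that regression is hardly needed is sound only if age and sex really are balanced. The protocol states that aim but gives recruiters nothing to carry it out. The three sources could easily supply children of different ages and sex mix across a range of 54 months.

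The ASD-TD contrast is the plan's test of whether its treatment targets are valid, and it decides whether ASD-DD is tested at all. If the groups differ in age or sex, the two variables the plan itself ranks highest could create or hide a group difference. No prespecified analysis would separate that from diagnosis. The same approach is to be applied to the app measures.

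**Working it through.** **1. The plan's own figure.** Inputs from Aim 1: 30 per group, TD SD 8, difference 7. The ASD SD, alpha and sidedness are not stated. I assume SD 8, 5% and two-sided.

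- Standard error = 8 × √(2/30) = 2.066.
- Noncentrality = 7 / 2.066 = 3.39; critical t (58 df) = 2.00.
- Power = 91.5%.

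The stated 90% is therefore reproduced. It is the power of an unadjusted test with no age or sex confounding.

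**2. Bias if balance fails.** The documents give no imbalance and no effect size. I assume:
- ages differ by 0.3 SD (if ages are uniform over 18-72 months, the SD is 54/√12 = 15.6, so about 4.7 months);
- one sex makes up 80% of one group and 50% of the other, which is 0.3/0.5 = 0.6 SD of a sex indicator with SD 0.5;
- age and sex together explain a share R² of the variance, split 80/20.

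Bias from age = 8 × √(0.8R²) × 0.3. Bias from sex = 8 × √(0.2R²) × 0.6.

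- R² = 0.1: age 0.68, sex 0.68, together 1.36 points.
- R² = 0.2: age 0.96, sex 0.96, together 1.92 points.
- R² = 0.3: age 1.18, sex 1.18, together 2.35 points.

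With this split the two parts are equal, so they cancel exactly when they act in opposite directions. The zero in that case follows from the inputs chosen.

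**3. Consequences.** Monte Carlo, 4,000-5,000 runs per cell: Welch t-test v linear model with age and sex and HC3 standard errors. The simulated biases agree with the formulas to within about 0.05 points.

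| Case | R² | Unadjusted | Adjusted |
|---|---|---|---|
| No true difference, effects aligned | 0.1 | 9.9% false positives | 4.6% |
| Same | 0.2 | 15.4% | 4.0% |
| Same | 0.3 | 20.2% | 4.9% |
| No true difference, sex only | 0.1 / 0.3 | 6.8% / 8.3% | 4.6% / 4.3% |
| No true difference, age only | 0.1 / 0.3 | 6.4% / 9.1% | 4.7% / 4.0% |
| No true difference, effects opposed | 0.1 / 0.3 | 4.9% / 5.2% | 4.9% / 4.6% |
| True difference 7, masked | 0.1 / 0.3 | 76.3% / 60.8% power | 87.2% / 94.3% |
| True difference 7, balanced on average | 0.1 / 0.3 | 92.1% / 91.0% power | 93.1% / 96.8% |
| True difference 7, pair-matched | 0.1 / 0.3 | 91.9% / 94.6% power | 92.6% / 97.3% |

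In the masked case the mean unadjusted estimate shrinks from 7 to 5.6 (R² 0.1) or 4.6 (R² 0.3). With balanced groups and a true difference of 5, power is 66-71% unadjusted and 67-81% adjusted.

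**The case against.** The best defence is that the plan already controls age and sex by design. It commits to balancing them, and in a combined protocol and SAP that commitment counts wherever it is written. Regression is then reserved for whatever remains. Covariates will be summarised by group, so imbalance should be visible, and a regression of outcome on group plus covariates is already in the plan. The larger false-positive rates assume that the planned balance fails and that both effects align. A smaller lapse does little harm: with 0.1 SD in age and 10 percentage points in sex, aligned, the bias is about 0.5-0.8 points and the false-positive rate about 5.5-7%. The plan is also cautious about covariates at 30 per group.

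Much of this stands. The intent to balance is real, the sizes are illustrative, and with good balance the unadjusted test is valid or conservative and merely less efficient. The pre-post regression is itself only exploratory and concerns a single arm.

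The gap remains. An intent with no procedure cannot be followed or audited. The group summaries do not name age and sex, and no rule says what follows if they differ. Adjustment chosen after seeing the outcomes would be post hoc. Two prespecified terms for 90 children are not the multiple-covariate modelling that the plan is wary of.

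**Conclusion.** The concern holds. Age and sex are named as the leading predictors besides group, no recruitment step balances them, and no prespecified group comparison adjusts for them. The power statement is not in error.

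The damage depends on imbalance and effect sizes that the documents do not give. Under the stated assumptions, bias ranges from about 0 (effects opposed) through 0.7-1.2 points (one variable imbalanced) to 1.4-2.3 points (aligned), against a design difference of 7. False positives range from 5% through 6-9% to 10-20%. Adjustment removes the bias when the age and sex effects are linear and common to the groups, keeps the error rate at 4-5%, and loses no power when the groups are balanced. The textual gap is certain; the sizes are illustrations. The change should be made, because it is worthwhile whether or not balance is achieved.

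**What to change.** **Analysis.** Make the primary analysis of IJA, RJA and joint engagement a linear model of outcome on group (ASD, DD, TD), age in months and sex, with heteroscedasticity-robust standard errors. Report ASD-TD first and then ASD-DD, keeping the existing gatekeeping and multiplicity adjustment. Keep the unadjusted t-test and the rank-based tests as sensitivity analyses. Check the common age slope with a group-by-age term.

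**Recruitment.** State how balance will be achieved, for example with age-band by sex targets for TD and DD that mirror the ASD group. This secures overlap in age, and the model deals with what imbalance is left.

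**Cost.** SAP wording and two model parameters. Age is already an eligibility criterion and sex is needed for the intended balancing, so no new data are required. Targets may slow TD and DD enrolment by an amount that cannot be estimated from the documents. Design & Procedures says "Baseline assessments of the TD and DD group will be on hold until COVID-19 in-person restrictions are lifted", so targets can be set for any children still to be assessed; the documents do not say how many remain. The model change is worth making even if targets prove impractical.

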Quantitative assessment of caregiver strategies at baseline and follow-up will be via the JERI, and include: (1) scaffolding, (2) following in on a child's focus, and (3) caregiver affect. These items will be scored on a Likert scale by a trained rater, from video-recorded caregiver-child interactions. We hypothesize that 12 sessions of NDBI-informed caregiver coaching will result in significant changes in the frequency and quality of caregiver strategies. Quantitative data will be analyzed with a paired t-test (or Wilcoxon rank-sum test if appropriate) to evaluate the change in caregiver strategies pre versus post intervention. In order to account for the estimated 15% attrition, and ensure a final total sample size of 30 caregiver-child dyads in the ASD group for the pre-post phase of the study, 35 caregiver-child dyads will initially be recruited. We will thus have 90% power to detect a standardized effect size (Cohen's d) of 0.60 using a paired t-test, assuming we standardize the difference between pre and post scores to have mean 0 and standard deviation 1.

Qualitative caregiver perceptions of strategies used during caregiver-child interactions will be collected at follow-up. Interview scripts will be developed to facilitate a broader understanding of strategies that are culturally-relevant to South African caregivers. Individual interviews will be audio-recorded. Data will be transcribed verbatim and cross-checked for accuracy, and inductively analyzed via content analysis utilizing NVivo.

Aim 4: Adapt the NDBI caregiver coaching intervention and assessment of caregiver NDBI strategies for telehealth delivery in order to maintain services for young children with ASD impacted by COVID-19. Explore the acceptability, feasibility, and appropriateness of the adapted intervention and assessment approach.

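### The severity question is tied to separate pre-post tests in high- and low-severity children, while the regression that would answer it is only optional

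*Combined protocol and SAP*

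**What the plan says.** The text is in Data Analysis & Statistical Considerations, in the Aim 1 discussion of the longitudinal phase. It covers both the exploratory digital outcomes of Aim 1 and the caregiver strategies of Aim 3.

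- **Reason for looking at severity:** "given that severity (measured by ADOS-2 comparison score) may predict changes over time".
- **Firm commitment:** data displays by severity category, and then "Likewise, we will perform inference separately for the high and low severity children". The test is the one planned for the whole group: "paired t-tests will be used, or if assumptions of the t-test are not met, the Wilcoxon signed rank test will be used".
- **Optional:** "We may explore regression modeling strategies where we regress change in each outcome measure on severity category (or severity score, if appropriate"), with possible adjustment for age and/or sex.
- **Reservation:** with 30 children, "we will be cautious when performing and interpreting our inferential statistics". The plan expects plots and summary statistics to carry much of the information.

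The plan gives no severity cut-off, no group sizes, no alpha for these tests and no rule for comparing the two groups' results.

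**The concern.** Whether severity predicts change is a question about a difference in change between severity levels. A pre-post test within each group compares that group with zero. Two such tests, however they come out, contain no test of the difference. The firm analysis therefore does not address its own reason, and the one that does is discretionary.

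The risk lies in how the results are read. If one group reaches significance and the other does not, it is natural to conclude that coaching works only in the first. With about half the sample in each group, that pattern is common even when the effect is the same in both. The study is meant to inform how treatment targets are tailored, so a false impression that severity matters could carry forward. Splitting the comparison score into two categories also discards information.

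**Working it through.** **Inputs from the plan.** Analysed sample: the plan aims to "ensure a final total sample size of 30 caregiver-child dyads in the ASD group", and for this "35 caregiver-child dyads will initially be recruited". Design effect (Aim 3): d = 0.60, with the standard deviation of change set to 1 and stated power of 90%.

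**Assumptions.** Two-sided alpha of 0.05. A 15/15 split, with 20/10 and 22/8 as alternatives. The d = 0.60 belongs to the Aim 3 caregiver strategies and is not given for the Aim 1 digital outcomes, so a range of d is shown.

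**1. The plan's own power figure.** For a paired t-test the noncentrality is d√n = 0.60 × √30 = 3.29 on 29 degrees of freedom, with critical value 2.045. Exact power is 88.8%. The normal approximation, Φ(3.29 − 1.96), gives 90.8%. The stated 90% is reproduced to within rounding.

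**2. Power within one severity group.** With n = 15 the noncentrality is 0.60 × √15 = 2.32 on 14 degrees of freedom, with critical value 2.145. Power is 58.0%.

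**3. How often the two tests disagree when severity is irrelevant.** With powers p1 and p2 in independent groups,

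P(exactly one significant) = p1(1 − p2) + p2(1 − p1).

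At 15/15 and d = 0.60 this is 2 × 0.580 × 0.420 = 48.7% (48.9% in 100,000 simulated trials). Both are significant in 34% and neither in 17%.

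| True d in both groups (15/15) | Exactly one significant |
|---|---|
| 0 | 9.5% |
| 0.2 | 19.8% |
| 0.3 | 31.0% |
| 0.4 | 42.3% |
| 0.5 | 49.2% |
| 0.6 | 48.7% |
| 0.7 | 40.9% |
| 0.8 | 29.4% |
| 1.0 | 9.7% |

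Uneven splits at d = 0.60:
- 20/10: 0.721 × 0.604 + 0.396 × 0.279 = 54.6%
- 22/8: 0.765 × 0.688 + 0.312 × 0.235 = 60.0%

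**4. A direct test of the difference.** This is a two-sample t-test on change scores, equivalent to regressing change on severity category. With 15 per group its noncentrality is δ/√(1/15 + 1/15) = 2.74δ on 28 degrees of freedom, where δ is the difference in mean change in SD units. When δ = 0 it is falsely positive in 5% (4.9% simulated). Its power is 35.5% at δ = 0.6 and 75.3% at δ = 1.0. It needs δ of about 1.06 for 80% power.

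**5. Continuous score against a direct high/low comparison.** Simulation with n = 30, bivariate normal data and assumed correlations between severity and change:

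| Correlation | Regression on score | Median split |
|---|---|---|
| 0.5 | 83% | 61% |
| 0.4 | 61% | 41% |

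The plan names no median split and no correlation. This comparison shows only what is lost by cutting the score in two; it does not describe the within-group tests.

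**6. Who has a score.** The COVID-19 adaptation lists the remote baseline measures by letter. Counting down the ASD baseline list, with JERI at n as the plan's note implies, the ADOS-2 is item d and is not among those letters. The Aim 4 description of remote baseline assessment does not mention it either. JERI, which supplies the Aim 3 outcomes, is in both remote batteries. Some remotely enrolled dyads may therefore have an Aim 3 outcome but no study ADOS-2 score, unless one is taken from earlier records.

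**The case against.** The strongest reply is that the plan already names the right analysis: the sentence after the firm commitment offers regression of change on severity. A reader might infer from the firm commitment that severity is examined only through separate tests; the documents do not support that. What stands is narrower: the direct analysis is optional and the separate tests are not.

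Second, the plan never says that p-values will be compared across groups, and it promises caution. Change within each group is a legitimate thing to describe. This stands too: the harm depends on an inference the plan does not state. But nothing in the plan warns against that inference, and the reason it gives for the analysis invites it.

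Third, a reader might infer that the tests contradict each other about half the time whatever the truth. They do not. The figure depends on an effect taken from Aim 3 and an assumed even split. Disagreement here means one test significant and the other not; significant results in opposite directions occurred in about 0.002% of simulated trials.

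Fourth, the direct analysis is itself weak at this size. That is correct. It favours reporting an estimate with its interval, which shows the imprecision, over two p-values, which hide it.

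**Conclusion.** The point holds in a limited form. The firm severity inference cannot show whether change differs by severity, and the analysis that can is left to discretion. At the plan's Aim 3 effect with an even split, exactly one of two equally effective groups would be significant in about 49% of trials, against a 5% error rate for a direct test. This rests on two-sided alpha of 0.05, equal true effects in both groups and group sizes the plan does not give; across the cases shown it runs from about 10% to 60%.

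The weight is small. The severity analysis is an addition with no hypothesis or power claim of its own, the Aim 1 part of it is exploratory, and the Aim 3 hypothesis concerns overall change. It does not follow that the overall pre-post tests or any co-primary endpoint are affected.

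**What to change.** Make regression of change on the continuous ADOS-2 comparison score the planned severity analysis for each outcome. State in advance whether it adjusts for age, sex or both, as the plan allows. Report the slope with its confidence interval. Keep the high/low plots, means and intervals as description, drop the within-group p-values, and fix any cut-off in advance. State how many children have a comparison score and how those assessed remotely are handled.

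The first cost is wording in the analysis section. The regression also assumes linearity, which plots of change against the score can check. The slope will be imprecise: about 61% power at an assumed correlation of 0.4 with all 30 children, and less if scores are missing. The restriction to children with a score is not a new cost, because the high/low analysis needs the same score.
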